9.7.5 Safety Variables

Safety will be assessed by:

- Adverse Events (AEs) including non-serious and Serious AEs, non-serious and Serious ADRs, AEs leading to treatment discontinuation and AEs leading to death at any time they become available.
- ADA, IRRs and Hypersensitivity (as identified risks)
- Acute renal failure, loss of consciousness and medication error (as potential risks)
- Vital signs (SBP, DBP, PR)
- Physical Examination
- Laboratory tests (haematology and chemistry)
- ECG

The proportion of patients experiencing at least one AE, non-serious and serious AEs, non-serious and serious ADRs, AE leading to treatment discontinuation and AEs leading to death will be provided. The above category of AEs will be summarized in terms of frequency of patients with at least one AE and in terms of number of events. These results will be provided by year from the baseline. The proportion of patients experiencing at least one AE will be calculated as the ratio between the number of patients experiencing at least one AE during the reference period and number of patients at risk (population at risk). In addition, incidence rates per person-time will be calculated as appropriate. Adverse events will be summarized by System Organ Class and Preferred Term using the MedDRA dictionary. The same approach will be followed also for identified and potential risks (see Section 11.1 for definition). For all the analyses outlined above, patients withdrawn from the study will be included: if they did not experience any events until their withdrawal they will be considered with no events for the examined period.

The duration of follow-up will be described.

Clinical Protocol Number: CLI-LMZYMAA1-12	
Clinical Protocol Version Number: 8.0	Date: 01 February 2019

The proportion of patients developing immunogenicity (as Anti-velmanase alfa-immunoglobulin G antibody in serum) will be also presented.

Vital Signs (SBP, DBP, PR) will be summarised by means of descriptive statistics. All variables (actual values and change from baseline, if applicable) will be presented by time point. In addition, the proportion of patients with substantial changes from baseline (i.e. >20mmHg for SBP and >10mmHg > for DBP) will be presented.

Physical examination (anthropometric measurements like height, weight, rate of growth and the ability to perform the endurance test) will be summarised by means of descriptive statistics. All variables (actual values and change from baseline, if applicable) will be presented by time point. The number and percentage of subjects able and not able to perform the endurance test will be produced.

Quantitative laboratory tests (haematology and chemistry) will be summarised by means of descriptive statistics. All variables (actual values and change from baseline, if applicable) will be presented by time point. All relevant clinical laboratory tests will be classified as Low NCS (non clinically significant)/Low CS (clinically significant), Normal, High NCS/High CS, or Normal/Abnormal NCS/Abnormal CS according to the normal ranges and investigator assessment. The number and percentage of subjects with values in each category will be produced.

ECG interpretations will be classified as Normal, Abnormal NCS and Abnormal CS. The number and percentage of subjects with values in each category will be produced.

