8. RESEARCH QUESTION AND OBJECTIVES

Primary Objective

- To assess the long-term effectiveness and safety of treatment with Lamzede under conditions of routine clinical care.
- In terms of effectiveness, the primary focus of the registry is to estimate the Global Treatment Response rate as percentage of patients qualified as responders by aggregately assessing oligosaccharides in serum (umol/L), (GTR-Pharmacodynamic Domain), 3MSCT (step/min), 6MWT (mt), FVC (% of predicted) (GTR-Functional Domain) and QoL based on CHAQ VAS-Pain and CHAQ- Disability Index (GTR-QoL Domain).
- In terms of safety, the rate of AEs (including ADA, IRRs and Hypersensitivity as identified risks) in the treated patients will be the main research of the study.

Secondary Objectives

- To characterize the alpha-mannosidosis population, including clinical manifestation, progression and natural history.
- In particular, oligosaccharides in serum (umol/L), endurance based on 3MSCT (step/min), 6MWT (m) and 2MWT (m) assessment, respiratory function through FVC (as litre and as percentage of predicted), hearing function with PTA, length and rate of infections (requiring or not antibiotics), rate of psychotic events, immunological status as per serum IgG, IgA and IgM, and QoL assessed by EQ-5D-5L, Zarit Burden Interview, CHAQ, Behavior Checklists (prescholar, scholar, adult and older adult) will be adopted for characterizing the alpha-mannosidosis population
- Rate of incidence of acute renal failure and loss of consciousness (as potential risks under Lamzede treatment), change in vital signs (SBP, DBP), laboratory tests (haematology and chemistry), physical examination and ECG will also be monitored.

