Laboratory chemistry ^{8b}		Х	X		X
Oligosaccharides in		Х	X		X
serum ^{7a}					

Clinical Protocol Number: CLI-LMZYMAA1-12

Clinical Protocol Version Number: 8.0

Date: 01 February 2019

Procedure	Registry Inclusion visit (approx 7 days)	Registry Baseline visit (Time 0)	Unscheduled Follow-up Routine Clinical Visits ¹	Six-month Follow-up Routine Clinical Visits ²	Yearly Follow-up Routine Clinical Visits
Serum Immunoglobulin class G, A, M ^{7a}		Х	X		X
Three-minute stair climbing test (3MSCT) ⁹ , when applicable		Х			X
Six-minute walk test (6MWT) ⁹ , when applicable		Х			X
Two-minutes walk test (2MWT) ¹⁰ , when applicable		X			X
Forced vital capacity (L and % of predicted)		Х	X		X
Electrocardiogram		Х	X		X
Hearing test (PTA)		Х	X		
Infections (including length and antibiotics requirement)		Х	X		X
Psychotic events		Х	X		X
Adverse Events /Adverse Drug Reactions ¹¹	X	Х	Х	Х	X
Health Assessment Questionnaires					
EQ-5D-5L		Х			X
Zarit Burden Interview		Х			X
CHAQ		Х			X
Behavior Checklists ¹²		Х			X

Abbreviations: ADA, anti-velmanase alfa-immunoglobulin G (IgG) antibody; CHAQ, Childhood Health Assessment Questionnaire; EQ-5D-5L, European Quality of Life Five Dimension Five Level Scale; L, litre; PTA, pure tone audiometry

1. Unscheduled follow-up visits can be performed at, but not limited to, three months after Lamzede treatment start, or whenever deemed appropriate according to treating physician's judgement for patients that start Lamzede treatment within one year prior to Registry inclusion.

2. Additional follow-up visit after six months is highly recommended for patients that start Lamzede treatment within one year prior to Registry inclusion.

- 3. If not taken or collected at Registry Inclusion visit.
- 4. Patients' retrospective data may be collected at the time of Registry enrolment if available. Baseline visits are recommended to be repeated for those patients who will start Lamzede therapy during the course of the study, before therapy is initiated.
- 5. Physical examination to collect vital signs, anthropometric measurements like height, weight, rate of growth and the ability to perform the endurance test at the study visit.
- 6. If applicable, information regarding weekly Lamzede therapy received by the patient need to be recorded within all the Registry duration

Clinical Protocol Number: CLI-LMZYMAA1-12	
Clinical Protocol Version Number: 8.0	Date: 01 February 2019

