9.3.2 Administration of Medication

The Registry is an observational study and for this reason no treatment will be administered per protocol requirement. Information concerning administration of medication will be collected from the practice of the routine clinical care. Details of weekly Lamzede therapy and concomitant therapies received by the patient either in hospital or in home infusion settings, where allowed per local practice, will be collected at baseline and within the overall duration of the study. Setting of treatment administration will be collected as well.

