9.7 Data Analysis

The following describes the statistical analysis as it is foreseen at the time of planning the trial. Detailed methodology for the summary and statistical analyses of data collected in this study will be documented in a Statistical Analysis Plan (SAP).

9.7.1 Populations for Analysis

The following analysis sets will be defined:

- The Lamzede Safety analysis set (L-SAF) will contain all enrolled patients fulfilling inclusion criteria who have, at some time, received Lamzede treatment. This will include all patients entering the study currently taking Lamzede and all patients not taking Lamzede on entry to the study, but who begin doing so during the study. The latter group (those not taking Lamzede on entry to the study, but who begin doing so during the study) will only be classed as in the L-SAF from the time that they begin taking Lamzede. As is common practice, patients who have taken any amount of Lamzede, even if only one dose, will be included in the safety analyses. With regards to L-SAF definition, a minimum individual follow up of 1 month after last dose taken will be proposed. A consequence of this approach, where patients can be in the L-SAF for very varying amounts of time is that adverse event (and adverse reaction) rates will be presented based on person-years at risk, and not simply based on the total number of patients who are ever in the L-SAF.
- The Lamzede Effectiveness analysis set (L-FAS) will contain patients included in the Lamzede Safety analysis set at the times when they have been taking Lamzede, and for 12 months thereafter excluding patients without any valid measurement and those with major protocol deviations affecting the effectiveness evaluations. The consequence of this is that

Clinical Protocol Number: CLI-LMZYMAA1-12	
Clinical Protocol Version Number: 8.0	Date: 01 February 2019

"baseline" will be clearly defined for each patient – namely the time they started to take Lamzede, not necessarily the time they enter the study. So a patient can be excluded from the L-FAS for some of their time in the study, and then join the L-FAS. In such cases, their "baseline" would be the time when they started.

- The No-Lamzede Safety analysis set (NL-SAF) will include patients only for the time when they are not (and have not within 1 month) been taking Lamzede.

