11.3 Intensity of Adverse Event

Each AE must be rated on a 3-point scale of increasing intensity:

- Mild: The event causes a minor discomfort, or does not interfere with daily activity of the patient, or does not lead to either modification of test treatment dosage or establishment of a correcting treatment.
- Moderate: The event perturbs the usual activity of the patient and is of a sufficient severity to make the patient uncomfortable. The event leads to a diminution of dosage of the test treatment, or a temporary interruption of its administration or to the establishment of a correcting treatment.
- Severe: The event prevents any usual routine activity of the patient and causes severe discomfort. It may be of such severity to cause the definitive interruption of test treatment.

Clinical Protocol Number: CLI-LMZYMAA1-12

Clinical Protocol Version Number: 8.0

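### Infusion-related reactions, part of the primary safety objective, get only patient and person-time measures; a rate per infusion given should be added from the weekly infusion records

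*Protocol*

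**What the plan says.** Protocol section 8 puts IRRs and hypersensitivity inside the primary safety objective: "the rate of AEs (including ADA, IRRs and Hypersensitivity as identified risks) in the treated patients will be the main research of the study".

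Section 9.7.5 then sets the measures, reported by year from baseline. The patient proportion is "the ratio between the number of patients experiencing at least one AE during the reference period and number of patients at risk (population at risk". Events are also counted, and for rates the section says: "In addition, incidence rates per person-time will be calculated as appropriate". The identified and potential risks receive the same treatment: "The same approach will be followed also for identified and potential risks (see Section 11.1 for definition". Section 9.7.1 is firmer about the denominator, saying that "adverse event (and adverse reaction) rates will be presented based on person-years at risk".

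Exposure is to be recorded closely. Section 9.3.2 has the sites collect "Details of weekly Lamzede therapy and concomitant therapies received by the patient either in hospital or in home infusion settings", and footnote 6 of Table 1 in section 9.2.6 says that, where applicable, "information regarding weekly Lamzede therapy received by the patient need to be recorded within all the Registry duration".

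Gaps in exposure are foreseen. Temporary interruption is one of the recorded actions after an adverse event (section 11.5). The definition of moderate intensity in section 11.3 includes it: "or a temporary interruption of its administration or to the establishment of a correcting treatment". Patients may also start or stop treatment at any time.

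On time at risk, section 9.7.1 gives the Lamzede safety set (L-SAF) a minimum follow-up of 1 month after the last dose but no end. The No-Lamzede safety set (NL-SAF) takes time more than 1 month off the drug.

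**The concern.** For most adverse events, a week on treatment is a fair unit of time at risk. For an IRR it is not, because a week without an infusion offers no opportunity for the event. A patient whose infusions are paused after a reaction, or who misses some in routine care, still adds person-time and still counts as one patient at risk. The yearly proportion and the person-year rate can then fall without any change in how well an infusion is tolerated.

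Section 9.7.5 reports these results year by year. A reader who sees the IRR rate decline over successive years could take it as growing tolerance when part or all of it is fewer infusions. The records that would separate the two explanations are already to be collected, but no analysis uses them.

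**Working it through.** **Plan's own figure.** The protocol gives no expected rate or precision for IRRs in the registry, so there is none to reproduce. The nearest figure is in section 7.1: IRRs in 9% of patients in the earlier programme of 33 patients, consistent with 3/33 = 9.1%.

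**Inputs.** Weekly infusions (section 9.3.2; Table 1, footnote 6), so 365.25/7 = 52.18 per year. One month is 365.25/(12 × 7) = 4.35 weeks. The risk per infusion, *p*, and the share of infusions missed, *m*, are not in the documents and are assumptions.

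**Formulas**, with constant *p* and independent infusions:

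- person-year rate = 52.18 × (1 − m) × p
- ratio to full exposure = 1 − m, whatever the value of *p*
- one-year proportion with at least one event = 1 − (1 − p)^(52.18 × (1 − m))
- rate per infusion given = p

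**Scattered missed infusions, with p = 0.5% assumed:**

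| Missed | Per 100 person-years | Ratio | One-year proportion | Per 1000 infusions |
|---|---|---|---|---|
| 0% | 26.1 | 1.00 | 23.0% | 5.0 |
| 10% | 23.5 | 0.90 | 21.0% | 5.0 |
| 25% | 19.6 | 0.75 | 17.8% | 5.0 |
| 50% | 13.0 | 0.50 | 12.3% | 5.0 |

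**Scale suggested by the protocol's 9%.** Suppose all of it fell within one year of full weekly dosing. Then p = 1 − 0.91^(1/52.18) = 0.18%, and the rate is 52.18 × 0.0018 = 9.4 per 100 person-years. In 70 patient-years (one year of the 70 treated patients assumed in section 9.5) that is about 6.6 events. With 10% of infusions missed it becomes 0.90 × 6.6 = 5.9, and with 25% missed 0.75 × 6.6 = 4.9. The earlier programme ran to 48 months, so the true yearly figure may be lower. By contrast, an assumed *p* of 1% would imply 1 − 0.99^52.18 = 40.8% of patients reacting each year, far above anything in the documents.

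**One pause within a year.** Infusions given are 52.18 − P for a pause of P weeks. Reading A lets person-time run on, so the ratio is (52.18 − P)/52.18. Reading B stops person-time 1 month after the last dose, as the NL-SAF definition suggests, so the ratio is (52.18 − P)/(52.18 − P + min(P, 4.35)).

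| Pause | A | B |
|---|---|---|
| 4 weeks | 48.18/52.18 = 0.92 | 0.92 |
| 13 weeks | 39.18/52.18 = 0.75 | 39.18/43.53 = 0.90 |
| 26 weeks | 26.18/52.18 = 0.50 | 26.18/30.53 = 0.86 |

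Up to 1 month the readings agree and the dilution is complete. Beyond that they diverge, and the protocol does not say which applies. The rate per infusion is unchanged in every row.

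**Cross-reference.** Section 9.7.5 sends the reader to section 11.1 for a definition. That section defines adverse event, adverse drug reaction, and serious and non-serious events. It does not define identified or potential risks, IRRs or hypersensitivity.

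**The case against.** The strongest reply is that section 9.7 describes the analysis as foreseen at planning and leaves detailed method to the SAP, which is not at hand and may add a rate per infusion. That limits the point but does not remove it: the protocol positively states that these risks follow the general approach, and section 9.7.1 names person-years as the basis.

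Second, fewer infusions really do mean fewer reactions per patient-year, so the planned measures answer a legitimate question about patient burden. This stands. A reader might infer that the person-year rate is wrong and should give way to the per-infusion rate; the documents do not support that.

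Third, the NL-SAF rule may remove most of a long pause from treated time. This also stands. It would be wrong to assume that a 13-week pause must lower that year's rate by 25%; under the 1-month reading the fall is 10%.

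Fourth, the expected numbers are small. On the 9% figure, 10% missed infusions changes the count by less than one event in 70 patient-years, so over one year the effect may not be visible. Over 15 years of follow-up it could matter more, but the documents give no adherence figures to size it.

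Two further inferences go too far. Safety comparisons between subgroups might seem to be at risk, but section 9.7.5 plans none; the optional subgroup analyses appear in section 9.7.4, on effectiveness. And the absence of an IRR case definition here does not show that none exists: Table 1 footnote 11 and section 9.3.3 tie event collection to the risk management plan categories, and that plan and the eCRF are not shown.

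**Conclusion.** The point holds as a missing measure. For IRRs the protocol fixes denominators that mix risk per infusion with the number of infusions given, and it does not use the infusion records that could separate them. At constant risk per infusion, the person-time rate falls to 0.90 and 0.75 of its full-exposure value at 10% and 25% missed infusions, whatever the underlying risk. For a 13-week pause the ratio is 0.90 or 0.75, depending on the unstated end of L-SAF at-risk time. The shares missed are assumptions; the direction is not.

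The argument applies directly to IRRs, and to hypersensitivity only so far as an infusion triggers the event. Nor would a per-infusion rate settle every question about trend: if patients who react stop treatment, later infusions come from more tolerant patients and that rate also falls. The wrong pointer to section 11.1 is a real but minor error. Overall this is an inexpensive improvement to a primary safety analysis; it does not invalidate the measures already planned.

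**What to change.** In Protocol section 9.7.5, keep the patient proportion and person-year rate and add beside them IRRs per 100 infusions given, overall and by year since first infusion. Report the same rate for hypersensitivity events linked to an infusion. State the number of infusions with incomplete records next to each rate.

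Correct the reference to section 11.1 so that it points to where the identified and potential risks are defined.

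The cost is one more denominator, from data that sections 9.2.6 and 9.3.2 already ask for, and one corrected reference. The downside is that the new rate is only as good as the infusion records: unrecorded infusions would inflate it, which is why the count of incomplete records belongs with it.

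### Patients who withdraw without an event are scored as event-free for the rest of the examined period, which biases the yearly AE proportions downward; the person-time rule for these patients is left unclear

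*Protocol*

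**What the plan says.** Section 9.7.5 of the protocol defines the proportion with at least one AE as the patients with an event during the reference period divided by the patients at risk. On the period it says: "These results will be provided by year from the baseline". The same approach is to be used for the identified and potential risks. On person-time it says: "In addition, incidence rates per person-time will be calculated as appropriate". It then adds: "For all the analyses outlined above, patients withdrawn from the study will be included", and, of those patients, "if they did not experience any events until their withdrawal they will be considered with no events for the examined period".

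Section 9.7.1, in defining the Lamzede safety set, notes that time in the set will vary widely. It draws this conclusion: "adverse event (and adverse reaction) rates will be presented based on person-years at risk, and not simply based on the total number of patients" (meaning all those ever in the set).

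Section 8 sets the safety objective: "In terms of safety, the rate of AEs (including ADA, IRRs and Hypersensitivity as identified risks) in the treated patients will be the main research".

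Under section 11.8, AEs are recorded from consent until participation ends. Sections 9.2.4 and 11.9 extend this only to new serious events that are considered related to Lamzede and that come to the investigator's knowledge.

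**The concern.** A patient who leaves in month four of a year without an event has been observed for four months. The rule keeps that patient in the denominator for the year and enters a definite non-event for the eight months that nobody observed. Non-serious events and unrelated serious events in that time would not reach the database. The proportion is therefore too low unless no withdrawn patient would have had a first event later in the period. It cannot be too high.

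The rule is also said to cover every analysis listed before it, and that list includes the person-time rates. In a rate, counting no event for such a patient is harmless if the patient's time stops at withdrawal. It is not harmless if the patient is credited with the full period. The text does not say which is meant.

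Finally, the two sections differ in how binding the person-year rate is: firm in 9.7.1, an optional addition in 9.7.5. AE occurrence is the registry's main safety question, and section 6 plans a report every year, so the same one-sided error would recur in each report.

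**Working it through.** **Figures in the plan.** The protocol gives no AE proportion, AE rate or withdrawal rate for this rule, so there is no figure of its own to reproduce on this point. Its only precision figures are the exact 95% limits for the treatment response in section 9.5 (70 patients). All five rows reproduce to three decimals, and nothing below depends on them.

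**Inputs.**
- True one-year risk p: 9% and 18%, borrowed from the adverse-reaction frequencies in section 7.1 (infusion-related reactions and weight increase). Those are earlier-trial frequencies, used here as assumed yearly risks. A further 50% is assumed.
- Yearly withdrawal w: 5%, 10% and 20%, all assumed.
- Constant hazards, with withdrawal independent of AE risk (assumed).

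**Formulas.** With h = -ln(1-p) and c = -ln(1-w), the expected proportion under the rule is

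h/(h+c) × [1 - exp(-(h+c))].

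The expected person-time to first event or withdrawal is [1 - exp(-(h+c))]/(h+c). First events divided by this time give back h.

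**One case in full (p = 0.18, w = 0.10).**
- h = 0.1985 and c = 0.1054, so h + c = 0.3038.
- 1 - exp(-0.3038) = 1 - 0.82 × 0.90 = 0.262.
- Reported proportion = (0.1985/0.3038) × 0.262 = 0.171, against a true 0.180.
- In 70 patients this is 12.0 instead of 12.6.
- Person-time = 0.262/0.3038 = 0.862; rate = 0.1711/0.862 = 0.1985; and 1 - exp(-0.1985) = 0.180. Stopping time at withdrawal recovers the true risk.

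**All yearly cases (relative shortfall in brackets).**

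| True risk | 5% withdraw | 10% withdraw | 20% withdraw |
|---|---|---|---|
| 0.09 | 0.0878 (2.5%) | 0.0855 (5.0%) | 0.0808 (10.2%) |
| 0.18 | 0.1756 (2.4%) | 0.1711 (4.9%) | 0.1619 (10.0%) |
| 0.50 | 0.4888 (2.2%) | 0.4774 (4.5%) | 0.4539 (9.2%) |

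The shortfall is close to w/2. The result hardly depends on the withdrawal model. With withdrawal uniform over the year, the expected proportion is (1-w)p + w[1 - (1-exp(-h))/h]. For p = 0.50 this gives 0.478 at w = 0.10 and 0.456 at w = 0.20.

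**If full-year time were credited to withdrawn patients.** An event rate would be multiplied by (1-exp(-c))/c. This is 0.05/0.0513 = 0.975, 0.10/0.1054 = 0.949 and 0.20/0.2231 = 0.896, so the rate would be about 2.5%, 5% and 10% too low.

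**If the rule were applied to one 15-year period.** With an assumed yearly AE risk of 2%, the true cumulative risk is 1 - 0.98^15 = 26.1%. The rule would give 21.2%, 18.6% and 13.6% at 3%, 5% and 10% yearly withdrawal, which is 19%, 29% and 48% too low. Section 9.7.5 states yearly results, so this only shows how the error grows with the length of the period.

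**The case against.** The strongest reply is that this affects a supporting descriptive table. Section 8 speaks of the rate of AEs, section 9.7.1 puts AE rates on person-years, and no section calls the proportion primary. A reader might infer that the primary safety measure is biased; the documents do not support that, because a rate with time stopped at withdrawal is unaffected. What stands against the reply is that section 9.7.5 neither stops the time nor makes the rate binding.

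A reader might also see a flat contradiction between sections 9.7.1 and 9.7.5. That goes too far. Section 9.7.1 rejects a denominator of everyone ever in the safety set. Section 9.7.5 divides by patients at risk within a period, reports by year, also counts events, describes the duration of follow-up and foresees person-time rates. The two sections differ in firmness.

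On size, a patient who has left is not naturally at risk in later years, so the effect is confined to the year of withdrawal. With 70 patients and a risk of 18%, the standard error is √(0.18 × 0.82/70) = 0.046, against a shortfall of 0.009 at 10% withdrawal. This is fair, although sampling error goes both ways and this error only one.

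It is tempting to add that the bias grows because patients leave over poor tolerability. The text gives this little support. A patient with an AE before leaving is already counted for the any-AE proportion. Stopping Lamzede is not withdrawal from the registry (section 9.1), and the reasons listed in section 9.2.4 do not include an AE.

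Finally, detail may be left to the statistical analysis plan. But this is a rule the protocol states, not a detail it omits.

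**Conclusion.** The point holds in a limited form. Section 9.7.5 fixes a rule that biases the yearly proportions with at least one AE downward, including those for identified and potential risks. The size is about half of the year's withdrawal proportion: some 2-2.5%, 5% and 9-10% in relative terms at 5%, 10% and 20% yearly withdrawal. These figures rest on assumed withdrawal rates and AE risks, constant hazards and withdrawal unrelated to AE risk. The direction does not rest on them. Larger shortfalls would need a multi-year reference period, which the protocol does not state.

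Person-time rates are sound only if time ends at withdrawal. The wording leaves that open and makes the rates optional, although section 9.7.1 promises them. This should be fixed; it does not undermine the registry.

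**What to change.** In section 9.7.5:
- Delete the rule for withdrawn patients without events.
- State that withdrawn patients count as at risk, and contribute person-time, only until withdrawal.
- Make incidence rates per person-year the main AE summary, without the qualifier, in line with section 9.7.1.
- Give the proportions with at least one AE as cumulative incidence with withdrawals censored and death as a competing event (Aalen-Johansen), or keep the simple proportions and label them as crude.

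The cost is one paragraph of text and slightly more, but standard, programming. No new data are needed. Reported risks will be slightly higher. Censoring does not remove the bias if withdrawal depends on AE risk, and the reports should say so.
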